2.1 Source(s) of Support

Type/Source	Grant Title	Name of PI on Grant	Status
Federal Agency NIH, National Cancer Institute (NCI)	Multilevel approaches for promoting physical activity in rural communities	[name]	AWARDED
Attachment Name	Category	Version	Date Attached
Rural_PA_Budget.docx	Grant from funding source or private foundation/association	1	02/05/18
Year_1_Rural_Communities_NIH_NOA_1R01CA211323-01A1.pdf	Grant from funding source or private foundation/association	1	02/05/18
PA Rural Communities_A1.docx	Grant from funding source or private foundation/association	1	02/05/18
R01_Rural PA final package.pdf	Grant from funding source or private foundation/association	1	09/11/18

3. Research Team

4.12 Will a Certificate of confidentiality be used for this research?
Yes, certificate automatically issued by funding agency

4.13 Does this project need to be registered on [ClinicalTrials.gov](https://clinicaltrials.gov)?
Yes

4.13.a Who is the Responsible Party for registering this study in ClinicalTrials.gov?
Principal Investigator

4.21 Mark all that apply to your study:

1. Protocol

1.1 Is there a separate, written protocol that will be submitted in addition to this form? (Note: a grant application is not considered to be a protocol)
No

1.2 Select up to three key words below that best describe this research study:
• Public Health

1.3 Provide a short summary/abstract of the purpose and procedures of the study proposed in this IRB application.

- DO NOT include information on studies not proposed in this application.
- Use LAY terminology only. This must be easily understandable by IRB community members and nonscientists.
- DO NOT cut and paste technical abstracts from source of support applications that may not be understood by a general audience.

Up to half of all cancer related deaths are preventable via evidence-based lifestyle changes such as increasing physical activity, enhancing nutrition, and reducing obesity.(1-3) Physical inactivity is a specific modifiable risk factor for breast and colon cancer.(4) Rates of physical inactivity are lower in rural communities as compared to their urban and suburban counterparts.(5) Nearly one-third of Missouri's population lives in rural counties,(6) and the "Bootheel" region suffers from a disproportionately high rate of cancer, in addition to physical inactivity and obesity.(7,8)

The purpose of the present study is to determine if a multilevel intervention (consisting of community events at local walking trails, formation of walking groups, and text messaging) will increase physical activity among rural residents. Intervention community members will receive the multilevel intervention while control communities will not. In the intervention communities, it is preferable for all participants to partake in all aspects of the intervention; however, not every person will partake in every level. We will create a dose-response variable hypothesizing participants who take part in all aspects of the intervention (i.e., attend walking events, takes part in walking groups, and receives text messages) will increase their physical activity more than people who engage in less of the intervention and those in control communities. As a part of the walking group formation in intervention sites, we will be utilizing the Stanford Healthy Neighborhood Discovery Tool application in order to receive feedback from participants related to the walking trails in their towns.

1.4 Specify your research question(s), study aims or hypotheses:
Test the independent and moderating effects of a multilevel intervention and the community environment on physical activity among rural residents.

1.5 Background and significance and/or Preliminary studies related to this project:
Key informant interviews were conducted in the intervention communities with three groups of people, walking trail users, walking trail non users, and stakeholders. We received feedback on the best methods by which to utilize local walking trails in the communities. Further, participants indicated to us their willingness to partake in future aspects of the study. Walking trail users and walking trail non users may be asked to participate as participants, while stakeholders may be asked to partake in a coalition to partner in increasing physical activity in rural southeast Missouri.

1.6 Literature cited/references (if attaching a grant enter N/A):

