1.7 Describe EACH of your participant populations

- Include description of any control group(s)
- Specify the Inclusion/Exclusion criteria for EACH group

Intervention community members will be selected from seven communities in southeastern Missouri (n=600). Control community members will be selected from seven communities in southeastern Missouri (n=600). Communities are matched based upon population, demographic makeup, and income; then, randomized to the control or intervention condition. Inclusion criteria for both groups are adults, able to consent (e.g., no known cognitive impairments), able to be physically active, residing in the targeted communities, and willing to complete a telephone survey at three time points.

1.8 Check all materials/methods that will be used in recruiting participants:

- Telephone script
- Website or Social Media (printed pages)
- Word of Mouth/Snowball sampling
- Referral
- Other Methods/Source - Address based sampling, Random digit dialing

Attachment Name	Category	Version	Date Attached
Heartland_Moves_Screenshot.JPG	Recruitment: Website	1	11/05/18
Flyer.rtf	Recruitment Script: Phone	1	03/27/19

1.10 Describe where the consent discussion will occur (check all that apply):

- By phone
- Other - At local events (e.g., health fairs, walking events)

1.11 Participants and/or their legally authorized representative will have (check all that apply to the consent process and explain process in Question 1.12 below):

- As much time as they desire to consider enrolling in the study, including:
 - An opportunity to thoroughly review the consent materials with knowledgeable members of the research team, and with family and/or friends as appropriate
 - Sufficient time to have all of their questions answered

1.12 Provide a description of the enrollment and consent process in sequential order and address EACH of the bulleted points below:

- Describe each study population separately including control population
- Describe when recruitment and consent materials are used
- Indicate how much time individuals will have to consider participation
- If eConsent will be used to obtain an electronic signature, describe how the eConsent will be presented to participants, how their questions will be answered and how the participant will receive a copy of the final, signed consent
- Describe the steps that will be taken by the research team to minimize the possibility of coercion or undue influence during the consent process

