1.20 What have you done to minimize any risks?

- No foreseeable risks

1.21 What are the potential benefits related to this project for:

- the participant (if any)
- benefits to society (if any)

An increase in physical activity may lead to improved health. The benefit to society is the project, if successful, has the potential to be scaled-up to reach a larger number of people.

1.22 Provide a summary of the analysis methods you will use, including, if applicable, the data points or outcomes you will analyze.

The intervention is at the community, interpersonal, and intrapersonal levels, and the activity environment is classified at the individual level. The basic model for the individual level analysis is: $Y_{jk} = \alpha_j + \beta I_{jk} + \gamma X_{jk} + \eta Z_{jk} + \theta I_{jk} * E_{jk} + \epsilon_{jk}$; where Y_{jk} is the change in physical activity for subject k in j th community ($j = 1, 2, \dots, 12$), $I_{jk} = 1$ if intervention and 0 otherwise, X = a vector of community level covariates, Z = a vector of individual level covariates (including E_{jk} individual level of activity environment), and $I_{jk} * E_{jk}$ = intervention-by-environment interaction. The parameter α_j is the random intercept, β is the main effect for intervention, and θ is the interaction effect. In this model, β is the expected difference in the physical activity level between intervention and control among those whose physical activity is mainly indoor, and $(\theta + \beta)$ is the expected difference in the physical activity level between intervention and control among those whose physical activity is mainly in the natural environment. Both main and

interaction effects are adjusted for community level and individual level covariates. The primary analyses will be conducted at the end of 1 and 2 year follow-up. In these analyses, baseline physical activity level will be used as one of covariates.

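### The planned dose-response comparison rests on self-selected uptake and has no stated method or exploratory label, so it can be expected to show a difference without any intervention effect if readiness to take part goes with activity change

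*Combined protocol and SAP*

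**What the plan says.** The lay summary in section 1.3 describes three components: community events on walking trails, walking groups and text messages. It accepts that "not every person will partake in every level". It then sets out the analysis, "We will create a dose-response variable hypothesizing participants who take part in all aspects of the intervention", with the prediction that they "will increase their physical activity more than people who engage in less of the intervention and those in control communities".

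Section 1.7 says that matched communities are "then, randomized to the control or intervention condition". No level of participation is assigned to individuals.

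Section 1.22 gives the analysis model. The outcome "is the change in physical activity for subject k in" a given community, and the coefficient on the 0/1 assignment indicator "is the main effect for intervention". The model also has an intervention-by-environment interaction and community and individual covariates, and "baseline physical activity level will be used as one of covariates". It has no term for dose. The aims in section 1.4 and the sample size in section 1.23 do not mention dose either.

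**The concern.** The hypothesis contains two contrasts: full participants against less-engaged participants, and full participants against everyone in the control communities. Randomisation protects neither. Full participants are a selected part of the intervention sample. Controls are the whole control sample, including people who would have taken part fully had they been offered the programme and people who would not.

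Those who turn up to events and join groups may be the people who were about to become more active anyway. If so, they would show a larger increase than either comparator with no help from the intervention. Adjusting for baseline activity deals with where people start, not with their readiness to change. In any case, section 1.22 states that adjustment for the main analyses, not for the dose comparison.

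What is at stake is interpretation. With a directional hypothesis on record, and no method or status attached to it, a null randomised result could be followed by a claim that the programme worked in those who took part fully.

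**Working it through.** **Step 1. The plan's own figure.** Section 1.23 gives means of 42.5 and 49.3 min/week (difference 6.8), SD 16, ICC 0.01 to 0.03, and 12 communities of 48, so 576 people or 288 per arm. The design effect is 1 + 47 × ICC = 1.47, 1.94 and 2.41 at ICC 0.01, 0.02 and 0.03. With 288 divided by the design effect as the effective number per arm, and two-sided 5%, the normal approximation gives power of 98.8%, 95.6% and 90.8%. The stated power above 90% is reproduced. It belongs to the randomised comparison, and no figure is given for dose. The 6.8 min/week serves below as a yardstick.

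**Step 2. Expected gap with no intervention effect.** Assumptions not in the document:
- each person has a normally distributed readiness to take part, with correlation r with change in activity, r = 0.1 to 0.4;
- the most ready 25% of the intervention sample are the full participants (f = 0.25).

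The mean readiness of the top quarter is φ(z)/f = 0.3178/0.25 = 1.271 SD units. Hence:
- full minus control = r × SD × 1.271;
- full minus less-engaged = the same value divided by (1 − f) = 0.75.

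The document gives no SD for change. Section 1.23 uses 16 for activity level, deliberately larger than the reported 6.2, so both are shown (min/week):

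| r | vs control, SD 16 | vs less-engaged, SD 16 | vs control, SD 6.2 | vs less-engaged, SD 6.2 |
|---|---|---|---|---|
| 0.1 | 2.0 | 2.7 | 0.8 | 1.1 |
| 0.2 | 4.1 | 5.4 | 1.6 | 2.1 |
| 0.3 | 6.1 | 8.1 | 2.4 | 3.2 |
| 0.4 | 8.1 | 10.8 | 3.2 | 4.2 |

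The gap against controls equals the planned 6.8 at r = 6.8/(16 × 1.271) = 0.33 for SD 16, but only at r = 6.8/(6.2 × 1.271) = 0.86 for SD 6.2.

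**Step 3. Sensitivity to the share of full participants.** With f from 20% to 50% and SD 16, the gap against controls is 2.5 to 4.5 at r = 0.2 and 3.8 to 6.7 at r = 0.3. Against the less-engaged it is 5.1 to 5.6 and 7.7 to 8.4.

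**Step 4. How often the contrast would be significant.** Simulation with zero effect, 12 communities, 576 people, ICC 0.03, f from 20% to 50%, community-level t-tests and 1,000 runs per setting:

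| r | full vs less-engaged | full vs control | all participants, randomised |
|---|---|---|---|
| 0 | 3–6% | about 5% | 4–5% |
| 0.1 | 14–20% | 7–11% | about 5% |
| 0.2 | 50–59% | 18–32% | 4–7% |
| 0.3 | 80–90% | 35–59% | 4–5% |

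The simulated outcome is simply proportional to the SD, so these rates do not depend on whether 16 or 6.2 is used. They do depend on the number of people and communities. The section 1.23 figures were used here, although section 1.7 lists seven communities per arm and section 1.13 an accelerometer subset of 300. That mismatch is a separate matter.

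**The case against.** The strongest reply is that the randomised comparison is already the specified analysis. Section 1.22 defines the intervention indicator by assignment, whatever the uptake, and plans its primary analyses on that model with baseline adjustment. Section 1.23 powers only that contrast and its environment interaction. The dose hypothesis appears once, in a summary that has to be in lay terms. This stands. A reader might infer that efficacy will be judged on dose, or that the primary analysis is compromised. The document supports neither reading.

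A reader might also infer that the comparison is bound to show a dose effect when the intervention does nothing. That goes too far: the document gives no correlation between uptake and change, and at r = 0 there is no bias. The direction is not certain either. Recruitment in section 1.12 includes existing trail users, who might take part fully yet have little room to increase.

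Two supporting arguments should not be used. Walking at events is part of the intervention, so extra walking there is a genuine effect; only activity that people would have done anyway is artefact. And nothing says whether texts are opt-in or sent to everyone enrolled, so receiving them cannot be counted as a sign of motivation.

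Finally, the sizes in minutes rest on assumed inputs. At SD 6.2 they are well under half of those at SD 16, and any baseline adjustment that lowers the residual SD would shrink them further.

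What survives is that a directional hypothesis is on record for a non-randomised contrast, with no method, adjustment or status stated.

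**Conclusion.** The point holds for the dose-response hypothesis in section 1.3 only. As written, it compares self-selected full participants with two groups that are not comparable to them, and nothing in the document deals with the selection or limits what may be concluded.

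If readiness to take part correlates with activity change, a difference can be expected with no intervention effect. Under the stated assumptions (25% full participants, r = 0.1 to 0.4), the spurious gap against controls is 2.0 to 8.1 min/week at SD 16 and 0.8 to 3.2 at SD 6.2, against a planned effect of 6.8. The upper range is large enough to be mistaken for the planned effect; the lower range is not. The correlation, the share of full participants and the SD of change are all assumptions. The primary randomised analysis in section 1.22 is unaffected. The change should be made, but it does not touch the trial's main inference.

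**What to change.** In sections 1.3 and 1.22:

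- State that conclusions on efficacy rest only on the randomised comparison of all participants in intervention communities with all participants in control communities, whatever their uptake. Section 1.22 already implies this; saying it settles the status of the dose analysis.
- Drop the unadjusted contrast of full participants with control communities.
- Keep dose-response as an exploratory, non-causal description within intervention communities, adjusted for baseline activity. Say that this adjustment does not remove selection on readiness to change. In the illustration, the contrast with less-engaged participants carries the larger bias, so this label matters.

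If a causal question about uptake is wanted, it needs its own pre-specified method, such as a complier-average or principal-stratification analysis with named baseline predictors of uptake. A complier-average analysis would have to face the likelihood that partial participation also has some effect. This is optional.

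The required change is wording only. The cost is the loss of one hypothesis that reads as confirmatory.

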1.7 Describe EACH of your participant populations

- Include description of any control group(s)
- Specify the Inclusion/Exclusion criteria for EACH group

Intervention community members will be selected from seven communities in southeastern Missouri (n=600). Control community members will be selected from seven communities in southeastern Missouri (n=600). Communities are matched based upon population, demographic makeup, and income; then, randomized to the control or intervention condition. Inclusion criteria for both groups are adults, able to consent (e.g., no known cognitive impairments), able to be physically active, residing in the targeted communities, and willing to complete a telephone survey at three time points.

1.8 Check all materials/methods that will be used in recruiting participants:

- Telephone script
- Website or Social Media (printed pages)
- Word of Mouth/Snowball sampling
- Referral
- Other Methods/Source - Address based sampling, Random digit dialing

Attachment Name	Category	Version	Date Attached
Heartland_Moves_Screenshot.JPG	Recruitment: Website	1	11/05/18
Flyer.rtf	Recruitment Script: Phone	1	03/27/19

1.10 Describe where the consent discussion will occur (check all that apply):

- By phone
- Other - At local events (e.g., health fairs, walking events)

1.11 Participants and/or their legally authorized representative will have (check all that apply to the consent process and explain process in Question 1.12 below):

- As much time as they desire to consider enrolling in the study, including:
 - An opportunity to thoroughly review the consent materials with knowledgeable members of the research team, and with family and/or friends as appropriate
 - Sufficient time to have all of their questions answered

1.12 Provide a description of the enrollment and consent process in sequential order and address EACH of the bulleted points below:

- Describe each study population separately including control population
- Describe when recruitment and consent materials are used
- Indicate how much time individuals will have to consider participation
- If eConsent will be used to obtain an electronic signature, describe how the eConsent will be presented to participants, how their questions will be answered and how the participant will receive a copy of the final, signed consent
- Describe the steps that will be taken by the research team to minimize the possibility of coercion or undue influence during the consent process

To recruit intervention community participants Washington University in St. Louis (WashU) project staff will reach out via telephone to those walking trail users and walking trail non users to determine their current interest in participating in this study (see section 1.5) using the telephone script. Further, WashU project staff will reach out to stakeholders to determine their interest in being a part of a coalition - in this capacity, project staff will use the informational sheet to reach out to stakeholder constituents to determine their interest in partaking in the study.

Recruitment in control communities is detailed elsewhere. Participants in both intervention and control communities may provide their consent immediately after asking any questions, or project staff can call the potential participant back at a later time (typically within a week). It will be stated to participants that participation is completely voluntary, and they are welcome to withdraw at any time.

1.13 Provide a detailed description in sequential order of the study procedures following the consent process - DO NOT cut and paste from the Consent Document.

Describe study populations separately if they will be participating in different procedures

DESCRIBE:

- Control populations, if applicable
- Any randomization, if applicable
- What participants will be asked to do/what happens in the study (in sequential order)
- The time period over which procedures will occur
- Long-term follow-up and how it occurs

Control and intervention participants will conduct a telephone survey at baseline and one follow-up timepoint (n=1241). A subset recruited from the baseline telephone survey, will wear an accelerometer and global positioning devices for one

week at baseline and one follow-up timepoint(n=300).

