1.23 Provide the rationale or power analysis to support the number of participants proposed to complete this study. This study uses a paired, group-randomized design. By using matching criteria, we will balance potential community-level confounding factors (e.g., community size, poverty level) with a gain in the statistical power [9,10]. Based on the literature, we estimated accelerometer-measured MVPA in the control group at 42.5 minutes per week (m/w). [9] In the intervention group, we assume a 16% increase (42.5*1.16 = 49.3), based on a recent meta-analysis [11]. We used a much larger SD of 16 rather than that reported (6.2) to ensure a sufficient sample size both for testing the intervention effect and for testing the intervention-by-environment interaction (moderation) effect. We assumed ICC estimates in the range of 0.01-0.03, based on our pilot studies and values of ICCs in the literature [12-18]. With 12 communities and an average of 48 study subjects in each (a total of 576 subjects for accelerometry), the study has power >90% with 2-sided $\alpha = 5\%$ to detect the mean difference in MVPA between the control (42.5) and intervention (49.3) groups, using Donner's method [19]. For intervention-by-environment interaction, we assume in the natural environment, the intervention and control difference is 57 m/w versus 44 m/w, and in the indoor environment, the difference is 43 m/w versus 41 m/w. Estimates of interaction are based on our pilot work and existing studies [20]. With a common SD in each of four subgroups = 10, we have 84% power to detect a significant interaction using factorial analysis of variance methods (F-test) adjusting for clustering (ICC = 0.03). Our simulation using two-level mixed effect models also indicates the power to detect the assumed interaction effect >90%. Our sample size is determined for accelerometry subjects at the end of Year 2. With a yearly follow-up rate of 80%, which is achievable given our previous work, we need to enroll 576/0.64 = 900 at baseline for accelerometry. For telephone survey subjects, we need to enroll 900/0.75 = 1,200 at baseline.

1.25 Will any data from this project be stored for use in future research studies?
No

1.26 Does this project involve the collection or use of biological samples or genetic data?
No

1.27 Are you requesting institutional certification to contribute human data or samples to a repository or database for broad sharing (public or restricted access)?
No

2. Participants

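### Section 1.23 bases its >90% power on 576 accelerometer completers (900 enrolled) in 12 communities, but 1.13 has 300 wearers and 1.7 has 14 communities; 300 does not secure 90%

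*Combined protocol and SAP*

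**What the plan says.** **Size basis (1.23).** The sample size is built on accelerometry: "Our sample size is determined for accelerometry subjects at the end of Year 2". The claim is "With 12 communities and an average of 48 study subjects in each (a total of 576 subjects for accelerometry), the study has power >90" percent, two-sided 5%, by Donner's method. Its inputs are 42.5 versus 49.3 minutes per week, SD 16, and ICC 0.01 to 0.03. With 80% followed each year, "we need to enroll 576/0.64 = 900 at baseline for accelerometry".

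**Procedures (1.13).** A subset of the telephone sample wears the devices for one "week at baseline and one follow-up timepoint(n=300"). The follow-up is not dated, and the text does not say whether 300 are enrolled or complete.

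**Communities.** Section 1.7 reads "Intervention community members will be selected from seven communities in southeastern Missouri (n=600") and "Control community members will be selected from seven communities in southeastern Missouri (n=600"), which makes 14. The model in 1.22 indexes communities 1 to 12, and 1.23 also uses 12.

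**Follow-up.** Section 1.22 says "The primary analyses will be conducted at the end of 1 and 2 year follow-up", and 1.7 asks for willingness to be surveyed three times. Section 1.13 has baseline and a single follow-up.

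**Interaction (1.23).** "With a common SD in each of four subgroups = 10, we have 84% power to detect a significant interaction" by an F-test with ICC 0.03. The next sentence reports over 90% for the same effect by simulation.

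**The concern.** The number of wearers is the quantity the trial was sized on, and two current sections disagree about it. Against enrolment the ratio is 900/300 = 3.0; against completers it is 576/300 = 1.9. On either reading 1.13 describes a smaller accelerometer study than the one whose power is quoted, and no section recalculates power for 300. A null accelerometer result would then be read against power that the described design does not secure over the plan's own ICC range.

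The community count and the follow-up schedule compound the problem, because both enter the calculation: clusters through the design effect, retention through the number analysed. What is affected is the power justification, not the validity of the effect estimate.

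**Working it through.** **Inputs, all from 1.23 unless noted.** Difference 49.3 − 42.5 = 6.8; SD 16; two-sided α 5%; ICC 0.01, 0.02, 0.03; N = 576 and k = 12 communities; equal arms. Alternatives: N = 300 (1.13) and k = 14 (1.7). Retention is 80% for one year or 0.8 × 0.8 = 64% for two, so 300 enrolled leaves 240 or 192.

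**Formulas.** DEFF = 1 + (N/k − 1) × ICC; SE = 16 × √(2 × DEFF/(N/2)); power = Φ(6.8/SE − 1.96). No gain from pair matching is added: 1.23 gives no matching correlation and its claim reproduces without one.

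**Step 1: the plan's own figure.** With N = 576 and k = 12, N/k = 48. At ICC 0.03, DEFF = 1 + 47 × 0.03 = 2.41, SE = 16 × √(2 × 2.41/288) = 2.070, 6.8/2.070 = 3.285, and power = Φ(1.325) = 90.7%. At ICC 0.01 and 0.02 the SEs are 1.617 and 1.857, and power is 98.8% and 95.6%. The >90% claim holds over the whole ICC range. The enrolment sums also hold: 576/0.64 = 900 and 900/0.75 = 1,200.

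**Step 2: the same method with 300.** Example with k = 14 and ICC 0.03: N/k = 21.43, DEFF = 1.613, SE = 16 × √(2 × 1.613/150) = 2.346, 6.8/2.346 = 2.898, power = Φ(0.938) = 82.6%.

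| Analysed | k | ICC 0.01 | ICC 0.02 | ICC 0.03 |
|---|---|---|---|---|
| 576 | 12 | 98.8% | 95.6% | 90.7% |
| 300 | 12 | 91.1% | 85.7% | 80.1% |
| 300 | 14 | 91.8% | 87.3% | 82.6% |
| 240 (80% of 300) | 12 | 85.5% | 80.0% | 74.8% |
| 240 | 14 | 86.3% | 81.7% | 77.1% |
| 192 (64% of 300) | 12 | 78.4% | 73.3% | 68.6% |
| 192 | 14 | 79.2% | 74.8% | 70.7% |

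With 300 analysed, power drops below 90% once the ICC exceeds 0.012 (12 communities) or 0.014 (14). At ICC 0.03, 90% needs 540 analysed in 12 communities or 451 in 14. Within the 300-wearer rows, two more communities add about 1 to 2.5 points.

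**Step 3: detectable difference at 80% power**, (1.960 + 0.842) × SE = 2.802 × SE, k = 14, ICC 0.01 to 0.03: 5.7 to 6.6 minutes per week with 300 analysed, 6.2 to 7.1 with 240, 6.9 to 7.6 with 192.

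**Step 4: interaction power (secondary).** The contrast is (57 − 44) − (43 − 41) = 11, with SD 10 and ICC 0.03. Effective N = 576/2.41 = 239. With four equal cells, SE = 10 × √(4/(239/4)) = 2.59, and the F-test gives 98.9%, not 84%. The document gives no indoor/natural split. Assumed splits of 30/70, 20/80 and 14/86 give 97%, 92% and 84%. With equal cells, 300 analysed in 14 communities gives 96%, so I do not claim that 84% needs 576. Section 1.23 also says SD 16 was chosen to cover both tests, yet the interaction calculation uses SD 10.

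**The case against.** **SD 16 is deliberately conservative.** Section 1.23 says so, against a reported 6.2. At SD 6.2 even 192 analysed in 12 communities at ICC 0.03 would exceed 99%, and that worst case keeps 90% up to an SD of about 12.1. This is true, but the >90% is stated for SD 16. If the sponsor wants to rely on a smaller SD, the plan has to say so.

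**Baseline adjustment is planned in 1.22 and is not credited here.** With a baseline correlation of 0.5 (an assumption; the document gives none), the SD becomes 16 × √0.75 = 13.9, and 300 analysed would give about 90% to 97%. The plan's own figure takes no such credit, so the mismatch stands. What follows is that the actual loss of power is uncertain.

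**300 may be an update.** The telephone count of 1,241 in 1.13, against 1,200 elsewhere, suggests that section may hold later numbers. That is an inference. If it is right, 1.23 is out of date and needs restating.

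**The interaction mismatch need not come from the split.** SD 16 with ICC 0.02 and equal cells also gives 83.9%. That departs from two printed inputs, but it shows that the cause cannot be settled from the text. The 84% and the >90% also come from different methods, so their difference alone is not an error. What stands is that 84% does not follow from SD 10 and ICC 0.03 with equal cells.

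**The normal approximation flatters a trial with few clusters.** Also true. With t on k − 2 df, 576 in 12 communities gives 84.1% at ICC 0.03, and 300 in 14 gives 76% to 87%. I kept the normal form because it is the one that reproduces the plan's claim.

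**Conclusion.** The concern holds and should be fixed. The number of accelerometer wearers, the number of communities and the follow-up schedule conflict across 1.7, 1.13, 1.22 and 1.23, and the >90% belongs to a design other than the one in 1.13.

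The right wording is that 300 does not secure 90%, not that power must fall below it: if all 300 are analysed and the ICC is near 0.01, power is about 91% to 92%. At ICC 0.02 or 0.03, or if 300 is enrolment with the plan's retention applied, it is below 90%, and as low as 68.6%. Having 14 communities instead of 12 does not make up the difference. These figures rest on difference 6.8, SD 16, equal arms, equal community sizes, a normal reference distribution and no credit for matching or baseline adjustment. The interaction point is secondary, and the conclusion on the main effect does not depend on it.

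**What to change.** 1. Reconcile 300 with 576/900, and 14 with 12 communities, across 1.7, 1.13, 1.22 (including the community index) and 1.23.
2. In 1.13, state whether 300 is enrolled or completing and when the single follow-up occurs. Align this with the 1- and 2-year analyses in 1.22 and the three surveys in 1.7, and use the matching retention in 1.23.
3. If 300 and 14 stand, restate main-effect power for ICC 0.03 to 0.01: 83% to 92% if 300 are analysed, 77% to 86% if 240, 71% to 79% if 192. Alternatively, give the detectable differences from Step 3. If t-based values are also given, say that the reference distribution has changed from the one behind the >90%. Any credit for matching or baseline adjustment needs its correlation stated.
4. For the interaction, state the environment split, SD and ICC used, explain the SD 16 sentence, and recompute.
5. If 300 or 14 is the error, correct 1.13 or 1.7 instead.

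**Cost.** Restating the power is wording only: no added participants, but a less favourable figure. If 300 is the error, 1.13 would commit the trial to 900 wearers, 900 − 300 = 600 more than the printed number. If 300 was meant as completers, implied enrolment is 300/0.80 = 375 or 300/0.64 = 469, and the gap is 525 or 431.
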